3.4 SAFETY MEASUREMENTS

3.4.1 Clinical and Laboratory Measurements for Safety

3.4.1.1 Adult Population

The long-term safety will be assessed by directed physical exam, standard laboratory safety tests, and collection of ECIs, AEs related to protocol-specified procedures (blood draw), and drug related SAE's at each visit as specified in the Study Flow Chart 1.7.1.

3.4.1.2 Pediatric Population

The long-term safety will be assessed by directed physical exam and collection of AEs related to protocol-specified procedures and drug-related SAEs at each visit as specified in the Study Flow Chart 1.7.2.

3.4.2 Recording Adverse Experiences (Adult and Pediatric Populations)

ECIs, as described in Section 3.4.3.2 will be collected in the adult population. In addition, any AEs related to protocol-specified procedures (blood draw) will be collected in adult and pediatric populations. All other AEs will not be collected in this long term follow-up study.

An AE is defined as any unfavorable and unintended change in the structure, function, or chemistry of the body temporally associated with the use of the SPONSOR's product, whether or not considered related to the use of the product. Any worsening (i.e., any clinically significant adverse change in frequency and/or intensity) of a preexisting condition which is temporally associated with the use of the SPONSOR's product, is also an AE.

Changes resulting from normal growth and development which do not vary significantly in frequency or severity from expected levels are not to be considered AEs. Examples of this may include, but are not limited to, teething, typical crying in infants and children, and onset of menses or menopause occurring at a physiologically appropriate time.

AEs may occur in the course of the use of a Merck product in clinical studies or within the follow-up period specified by the protocol, or prescribed in clinical practice, from overdose (whether accidental or intentional), from abuse, and from withdrawal.

AEs may also occur in screened subjects during any preallocation baseline period as a result of a protocol-specified intervention including washout or discontinuation of usual therapy, diet, placebo treatment, or a procedure.

Such events will be recorded at each examination on the AE case report form (CRF)/Worksheets.

3.4.3 Immediate Reporting of Adverse Events to the SPONSOR

3.4.3.1 Serious Adverse Events (Adult and Pediatric Populations)

The following will be collected during the study:

- Drug related SAEs.
- All deaths of any cause will be collected.
- Any SAE considered by an investigator who is a qualified physician to be possibly, probably, or definitely related to the investigational product that is brought to the attention of the investigator at any time outside of the time period specified in the previous paragraph also must be reported immediately to one of the individuals listed on the sponsor contact information page found in the administrative binder.

All subjects with SAEs must be followed for outcome.

Note: Any drug-related SAE, or death due to any cause, which occurs to a subject must be reported within 24 hours to one of the individual(s) listed on the contact information page.

3.4.3.2 Events of Clinical Interest

3.4.3.2.1 Adult Population

ECIs will be recorded on the AE CRFs/Worksheets. ECIs defined for this protocol include:

- Spontaneous bacterial peritonitis;
- Variceal bleeding;
- Ascites;
- Encephalopathy;
- Hepatorenal syndrome;
- Hepatocellular carcinoma; - Any hepatocellular carcinoma that occurred and was not previously reported in the prior treatment study should be reported as an ECI;
- Liver transplant;
- Kidney transplant (PN052 subjects only) – any kidney transplant that occurred and was not previously reported in the prior treatment study should be reported as an ECI;
- Decreased eGFR calculated by the Modification of Diet in Renal Disease equation (PN052 subjects) will be analyzed for change from baseline in PN052;
 - For this study a decrease in eGFR is defined for subjects not on dialysis as:
 - CKD4 (15 to 30 ml/min/1.73 m²) in PN052 and is now CKD5 (<15 ml/min/1.73 m²),
 - CKD5 without dialysis in PN 052 and is now CKD5 with dialysis, OR
 - CKD4 in PN 052 and initiates dialysis
- New onset diabetes (PN052 subjects only);
- Cryoglobulinemia (PN052 subjects only);
- Cardiovascular disease limited to angina and myocardial infarction;
- Neurologic disorders limited to TIA or stroke;
- Graft rejection in subject who has undergone liver or kidney transplantation; or
- Post transplantation glomerulonephritis (PN052 subjects only).

3.4.3.2.2 Pediatric Population

No ECIs are defined for pediatric subjects and will not be collected.

3.4.4 Evaluating Adverse Events (Adult and Pediatric Populations)

Refer to [Table 6](#) for instructions in evaluating AEs.

Table 6

Instructions for Evaluating Adverse Events

Maximum Intensity	Mild	awareness of sign or symptom, but easily tolerated (for pediatric studies, awareness of symptom, but easily tolerated)
	Moderate	discomfort enough to cause interference with usual activity (for pediatric studies, definitely acting like something is wrong)
	Severe	incapacitating with inability to work or do usual activity (for pediatric studies, extremely distressed or unable to do usual activities)
Seriousness	A serious adverse experience is any adverse experience occurring at any dose that:	
	† Results in death; or	
	† Is life threatening; or places the subject/patient, in the view of the investigator, at immediate risk of death from the experience as it occurred [Note: This does not include an adverse experience that, had it occurred in a more severe form, might have caused death.]; or	
	† Results in a persistent or significant disability/incapacity (substantial disruption of one's ability to conduct normal life functions); or	
	† Results in or prolongs an existing inpatient hospitalization (hospitalization is defined as an inpatient admission, regardless of length of stay, even if the hospitalization is a precautionary measure for continued observation.) (Note: Hospitalization [including hospitalization for an elective procedure] for a preexisting condition which has not worsened does not constitute a serious adverse experience.); or	
	† Is a congenital anomaly/birth defect (in offspring of subject/patient taking the product regardless of time to diagnosis); or	
	Is a cancer; or	
	Is an overdose (Whether accidental or intentional.) Any overdose whether or not associated with an adverse experience must be reported within 24 hours.	
	Other important medical events that may not result in death, not be life threatening, or not require hospitalization may be considered a serious adverse experience when, based upon appropriate medical judgment, the event may jeopardize the subject/patient and may require medical or surgical intervention to prevent one of the outcomes listed previously (designated above by a †).	
Duration	Record the start and stop dates of the adverse experience. If less than 1 day, indicate the appropriate length of time and units	
Action taken	Did the adverse experience cause the test drug to be discontinued?	
Relationship to test drug	Did the test drug cause the adverse experience? The determination of the likelihood that the test drug caused the adverse experience will be provided by an investigator who is a qualified physician. The investigator's signed/dated initials on the source document or worksheet, that supports the causality noted on the AE form, ensures that a medically qualified assessment of causality was done. This initialed document must be retained for the required regulatory time frame. The criteria below are intended as reference guidelines to assist the investigator in assessing the likelihood of a relationship between the test drug and the adverse experience based upon the available information. The following components are to be used to assess the relationship between the test drug and the AE; the greater the correlation with the components and their respective elements (in number and/or intensity), the more likely the test drug caused the adverse experience (AE):	
	Exposure	Is there evidence that the subject/patient was actually exposed to the test drug such as: reliable history, acceptable compliance assessment (pill count, diary, etc.), expected pharmacologic effect, or measurement of drug/metabolite in bodily specimen?
	Time Course	Did the AE follow in a reasonable temporal sequence from administration of the test drug? Is the time of onset of the AE compatible with a drug-induced effect?
	Likely Cause	Is the AE not reasonably explained by another etiology such as underlying disease, other drug(s)/vaccine(s), or other host or environmental factors

Relationship to test drug (continued)	The following components are to be used to assess the relationship between the test drug and the AE: (continued)	
	Dechallenge	Was the dose of test drug discontinued or reduced? If yes, did the AE resolve or improve? If yes, this is a positive dechallenge. If no, this is a negative dechallenge. (Note: This criterion is not applicable if: (1) the AE resulted in death or permanent disability; (2) the AE resolved/improved despite continuation of the test drug; or (3) the study is a single-dose drug study.)
	Rechallenge	Was the subject/patient reexposed to the test drug in this study? If yes, did the AE recur or worsen? If yes, this is a positive rechallenge. If no, this is a negative rechallenge. (Note: This criterion is not applicable if: (1) the initial AE resulted in death or permanent disability, or (2) the study is a single-dose drug study.) NOTE: IF A RECHALLENGE IS PLANNED FOR AN ADVERSE EVENT WHICH WAS SERIOUS AND WHICH MAY HAVE BEEN CAUSED BY THE TEST DRUG, OR IF REEXPOSURE TO THE TEST DRUG POSES ADDITIONAL POTENTIAL SIGNIFICANT RISK TO THE SUBJECT/PATIENT, THEN THE RECHALLENGE MUST BE APPROVED IN ADVANCE BY THE U.S. CLINICAL MONITOR AND THE INSTITUTIONAL REVIEW BOARD/INDEPENDENT ETHICS COMMITTEE.
	Consistency with Study Drug Profile	Is the clinical/pathological presentation of the AE consistent with previous knowledge regarding the test drug or drug class pharmacology or toxicology?
The assessment of relationship will be reported on the case report forms /worksheets by an investigator who is a qualified physician according to his/her best clinical judgment, including consideration of the above elements.		
Record one of the following:		Use the following scale of criteria as guidance (not all criteria must be present to be indicative of a drug relationship).
Yes, there is a reasonable possibility of drug relationship.		There is evidence of exposure to the test drug. The temporal sequence of the AE onset relative to the administration of the test drug is reasonable. The AE is more likely explained by the test drug than by another cause. Depending on data collection method employed, drug relationship may be further graded as follows:
	Definitely related	There is evidence of exposure to the test drug. The temporal sequence of the AE onset relative to administration of the test drug is reasonable. The AE is more likely explained by the test drug than by another cause. Dechallenge is positive. Rechallenge (if feasible) is positive. The AE shows a pattern consistent with previous knowledge of the test drug or test drug class.
	Probably related	There is evidence of exposure to the test drug. The temporal sequence of the AE onset relative to administration of the test drug is reasonable. The AE is more likely explained by the test drug than by another cause. Dechallenge (if performed) is positive.
	Possibly related	There is evidence of exposure to the test drug. The temporal sequence of the AE onset relative to administration of the test drug is reasonable. The AE could have been due to another equally likely cause. Dechallenge (if performed) is positive.
No, there is not a reasonable possibility of drug relationship		Subject did not receive the test drug OR temporal sequence of the AE onset relative to administration of the test drug is not reasonable OR there is another obvious cause of the AE. (Also entered for a subject with overdose without an associated AE.) Depending on data collection method employed, drug relationship may be further graded as follows:
	Probably not related	There is evidence of exposure to the test drug. There is another more likely cause of the AE. Dechallenge (if performed) is negative or ambiguous. Rechallenge (if performed) is negative or ambiguous.
	Definitely not related	The subject/patient did not receive the test drug. OR Temporal sequence of the AE onset relative to administration of the test drug is not reasonable. OR There is another obvious cause of the AE.

3.4.5 SPONSOR Responsibility for Reporting Adverse Events (Adult and Pediatric Populations)

All AEs will be reported to regulatory agencies, IRB/IECs, and investigators in accordance with all applicable global laws and regulations.

3.5 STATISTICAL ANALYSIS PLAN (SAP)

This section outlines the statistical analysis strategy and procedures for the study. If, after the study has begun, changes are made to primary and/or key secondary objectives, or the statistical methods related to those objectives, then the protocol will be amended (consistent with International Committee on Harmonisation [ICH] Guideline E-9). Changes to exploratory or other non-confirmatory analyses made after the protocol has been finalized, along with an explanation as to when and why they occurred, will be listed in the clinical study report (CSR) for the study. Post hoc exploratory analyses will be clearly identified in the CSR. No separate SAP will be issued for this study.

3.5.1 Responsibility for Analyses/In-House Blinding

The statistical analysis of the data obtained from this study will be the responsibility of the Clinical Biostatistics department of the SPONSOR.

This study is being conducted as a long-term follow-up study during which no study treatment will be administered.

3.5.2 Estimation

Objectives of the study are stated in Section 2.1.

3.5.3 Analysis Endpoints

Efficacy and safety endpoints that will be evaluated are listed below.

3.5.3.1 Efficacy and RAS Endpoints

3.5.3.1.1 Adult Population

The primary efficacy endpoint in the adult population is the durability of long-term SVR which will be evaluated based upon the time to viral relapse. Viral relapse is defined as any subject who has confirmed HCV RNA \geq LLoQ and had achieved SVR in the follow-up in the prior treatment study (see Section 2.5). Relapse would be indicated so long as this was the same genotype of the virus seen in the prior treatment study (e.g. not a new infection or re-infection (see Section 2.5). Time to relapse is defined as the time from last dose of study therapy taken in the prior treatment study until the date where HCV RNA is \geq LLoQ. The percentage of subjects who remain HCV RNA $<$ LLoQ during the course of this study will also be estimated.

In adult subjects with HCV RNA \geq 1000 IU/mL at entry or during the study period, HCV sequence analysis will be performed to evaluate the presence of RASs and the persistence of RASs over time.

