2.3 SUBJECT EXCLUSION CRITERIA (ADULT AND PEDIATRIC POPULATIONS)

Exclusion criteria apply to both the adult and pediatric populations.

1. **Adult subjects:** In the opinion of the investigator, subject is mentally or legally incapacitated at entry into PN017.

Pediatric subjects: The subject has significant emotional problems or a clinically significant psychiatric disorder that may interfere with participant treatment, assessment, or compliance with the protocol.

2. Subject has received HCV therapy after completion of the prior treatment study and before entry into PN017.
3. Starting with AM 03: subjects who failed therapy due to re-infection, defined as:
 - an HCV RNA sample with a different genotype than the baseline genotype in the prior treatment study, or

- an HCV RNA sample determined to be reinfection by phylogenetic analysis with comparison to the baseline sequence in the prior treatment study.

4. Starting with AM 03: subjects who failed therapy in the prior treatment study and received retreatment with HCV therapy.

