2.5 LIST OF EFFICACY/PHARMACOKINETIC/IMMUNOGENICITY MEASUREMENTS

The following measurements are applicable for the adult and pediatric populations.

HCV Genotype

Samples will be genotyped using the Food and Drug Administration (FDA) approved Abbott HCV Real Time Genotype II assay which detects HCV GT1a, 1b, 2, 3, 4, 5, and 6 through the use of genotype-specific fluorescent-labeled oligonucleotide probes in a real-time reverse transcriptase-polymerase chain reaction (RT-PCR) assay. The RT-PCR reaction uses 3 sets of HCV specific amplification primers targeting the conserved 5' untranslated region (for all genotypes) and NS5B regions from GT1a and 1b. The assay has accuracy of >96% for GT1, 1a, 1b, 2, 3 and 4, 89% for GT5 and 83% for GT6 with 100% specificity in HCV serologically negative plasma samples. Phylogenetic analyses will be performed using sequences for NS3/4A, NS5A and NS5B to ensure accurate assignment of sample genotype/subtype.

HCV RNA

HCV RNA in plasma will be measured using a COBASTTM AmpliPrep/COBASTTM TaqmanTM HCV Test, v2.0 ® assay with a LLoQ of 15 IU/mL. HCV RNA definitions are presented in [Table 1](#).

Table 1

HCV RNA Definitions

Abbreviation	Definition	HCV RNA Level
TND	Target not detected	HCV RNA not detected
TD(u)	Target detected, unquantifiable	HCV RNA < LLoQ
TD(q)	Target detected, quantifiable	HCV RNA ≥ LLoQ

HCV=hepatitis C virus; LLoQ=lower limit of quantification; RNA=ribonucleic acid

For subjects enrolled prior to AM 03, durability of virologic response will be assessed in all subjects who are HCV RNA <LLoQ (either TND or TD[u]) on Day 1 of entry into this protocol and excluding any subject who is TND/TD(u) due to having received an anti-viral treatment after having failed previous therapy in the parent study.

Failure of therapy due to relapse more than 24 weeks after the end of therapy (termed late relapse) in this group of subjects will be measured as an HCV RNA that is confirmed to be ≥LLoQ and is not due to a new infection or re-infection. Confirmation is defined as an HCV RNA that is target detected, quantifiable (TD[q]) from a separate blood draw repeated in approximately 4 weeks.

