2.7.3 Analysis of Resistant Associated Substitutions

2.7.3.1 Adult Population

The evaluation of antiviral resistance to GZR will be obtained on subject samples with HCV RNA \geq 1000 IU/mL at study entry or during the course of this study; the presence of RASs and the persistence of RASs over time will be summarized using descriptive statistics, with subgroup analyses by class of regimen (e.g. NS3/4A inhibitors, NS5A inhibitors and NS5B inhibitors) as well as by specific components (Table 3). Only subjects who experienced virologic failure (other than reinfection) will be included in these analyses.

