 - If a subject achieved SVR at the end of follow-up in the prior treatment study and, is tested and found to have HCV RNA quantifiable during this study, that first sample with quantifiable HCV RNA will be tested for HCV GT. This is performed to determine if this is a relapse of the primary infection or a re-infection.
 - Plasma samples for HCV GT must be obtained and processed as instructed by the central laboratory.

Table 5

Actions and Interpretations Based on HCV RNA Results of Scheduled and Viral Confirmation Visits

Scheduled Visit Result	Action	Result of Viral Confirmation	Interpretation
TND	None	N/A	SVR
TD(u)	None	N/A	SVR
TD(q) Not previously determined to be a relapse, e.g. first time HCV RNA quantifiable	Viral Confirmation Visit	TND/TD(u)	SVR
		HCV RNA quantifiable	Relapse

HCV=hepatitis C virus; N/A=not applicable; RNA=ribonucleic acid; SVR=sustained virologic response; TND=target not detected; TD(q)=target detected, quantifiable; TD(u)=target detected but unquantifiable

Blood volumes collected at each visit are detailed in Appendix 6.2.1.

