3.5.5.1 Statistical Methods for Efficacy Analyses

3.5.5.1.1 Adult Population

The efficacy endpoint of time to viral relapse will be summarized using Kaplan-Meier methodology at fixed time points (6-month intervals). These time points represent the follow-up time since the last dose of study therapy taken in the prior treatment study. Subjects who do not relapse during the current study will be censored on the last visit date. Any subject who relapsed between the end of the prior treatment study and entry into this study will be considered a relapse at the time of study entry.

Relative days ranges, calculated from the date of last dose of therapy taken in the prior treatment study, will be used to define the months of follow-up for the analysis of time to viral relapse. These relative day ranges will be continuous and stretch from the date of last dose in the prior treatment study to the midpoint between the first 2 time points (i.e. 6 and 12 months --> midpoint: 9 months), from midpoint to midpoint between each successive pair of time points and above the last midpoint for the last time point. As the screening visit could occur within 1-year of the last dose of therapy taken in the prior treatment study for subjects enrolled prior to AM 03, certain subjects may have a follow-up time close to 6 years. Day ranges are therefore defined up to Month 72 and are provided in [Table 7](#).

Table 7

Definition of Months of Follow-up for Time to Relapse Analysis

Month	Relative Day Range ^a
6	1 to 274
12	275 to 456
18	457 to 638
24	639 to 821
30	822 to 1003
36	1004 to 1186
42	1187 to 1368
48	1369 to 1550
54	1551 to 1733
60	1734 to 1915
66	1916 to 2098
72	≥ 2098

^a Day range relative to date of last dose of therapy taken in the prior treatment study.

Missing Values

Only observed data will be included in the analyses. For the time to relapse analysis, subjects missing an HCV RNA evaluation at any particular visit will be considered a non-relapser for that visit. Subjects who discontinue the study without relapsing will be censored at the time of discontinuation.

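### Genotype is the only test tied to the relapse endpoint, so the plan cannot deliver its own exclusion of all reinfection

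*Combined protocol and SAP*

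**What the plan says.** Section 2.1.1.1 makes durability of response the first primary objective in adults, and Section 3.5.3.1.1 measures it by time to viral relapse. These places bear on what counts as relapse:

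- **Section 3.5.3.1.1** takes a confirmed HCV RNA at or above LLoQ after SVR and adds: "Relapse would be indicated so long as this was the same genotype of the virus seen in the prior treatment study". A parenthesis in the same sentence says that new infection and re-infection are not meant, and points to Section 2.5.
- **Section 2.5** requires that a late relapse "is not due to a new infection or re-infection", but attaches no test to that condition. It says the genotype assay "detects HCV GT1a, 1b, 2, 3, 4, 5, and 6", and that phylogenetic analyses are run "to ensure accurate assignment of sample genotype/subtype".
- **Section 3.3.1.1** has the first quantifiable sample after SVR genotyped and gives the reason: "This is performed to determine if this is a relapse of the primary infection or a re-infection".
- **Tables 2 and 5** read a confirmed quantifiable result as relapse and have no line for reinfection.

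A second test appears in exclusion criterion 3 (Section 2.3). There, reinfection is either a different genotype or "an HCV RNA sample determined to be reinfection by phylogenetic analysis with comparison to the baseline sequence in the prior treatment study". This is an eligibility rule, in force from Amendment 03, for subjects who failed therapy in the prior study.

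For the Kaplan-Meier analysis, Section 3.5.5.1.1 states: "Subjects who do not relapse during the current study will be censored on the last visit date". It has no separate rule for a subject found to be reinfected.

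**The concern.** Durability means that the original infection does not return. A new infection after cure says nothing about it, and the plan agrees, since it means to keep reinfection out of the event. The test it names can do that only when the new virus has a different genotype. A same-genotype reinfection looks exactly like a relapse on that test and would be counted as loss of response, which understates durability.

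The censoring rule works the other way. A subject whose reinfection is recognised has not relapsed, so remains in the relapse-free denominator until the last visit, although the new virus is already present. That tends to overstate durability.

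Section 3.5 says that no separate SAP will be issued and that changes to methods for primary objectives go through a protocol amendment. The rule therefore has to be settled in this document.

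**Working it through.** The plan states no sample size, event count or reinfection rate, so there is no figure to reproduce. The check sets the passages side by side.

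**1. Which test reaches the endpoint?** Sections 3.3.1.1 and 3.5.3.1.1 name genotype. Section 2.5 names no test in its late-relapse definition, and its phylogenetic analyses serve genotype and subtype assignment. Sequencing in Section 3.5.3.1.1 is for resistance-associated substitutions. The comparison with the subject's own baseline sequence in criterion 3 is not cited in any of these places, nor in Section 3.5.5.1.1.

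**2. How is each confirmed rebound after SVR classified?** The assay reports seven categories (1a, 1b, 2, 3, 4, 5, 6). Its result alone cannot separate relapse from reinfection within the subject's own category.

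| True state | Section 3.5.3.1.1 | Section 2.5 | Result |
|---|---|---|---|
| Reinfection, different genotype | Not relapse | Not relapse | Consistent |
| Relapse, same genotype | Relapse | Relapse | Consistent |
| Reinfection, same genotype, not recognised | Relapse | Relapse, as nothing shows otherwise | False event |
| Reinfection, same genotype, recognised by other means | Same-genotype clause: relapse. Parenthesis: not relapse | Not relapse | Conflict |

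**3. What happens to a recognised reinfection in the Kaplan-Meier analysis?** Let n subjects be at risk at an event time with d relapses, and let m of the n already carry a recognised new virus. These m subjects can no longer show a first rise above LLoQ. The planned factor is 1 − d/n. With them removed it is 1 − d/(n − m), which is smaller whenever d > 0. Leaving them in therefore raises the relapse-free estimate, but only if relapses occur later while they are still counted.

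As an illustration for one subject on the nominal schedule in Section 1.7.1, with the new virus found at Month 6, no retreatment and full follow-up:

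- PN052 subject: 60 − 6 = 54 months of extra time at risk.
- Three-year subject: 36 − 6 = 30 months.

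**4. How large is the misclassification?** With R reinfections, of which a share s have the same genotype and none is recognised by other means, the false events number R × s. Neither R nor s is in the documents. Purely as an assumption, R = 10 gives 10 × 0.25 = 2.5 events at s = 0.25 and 10 × 0.75 = 7.5 events at s = 0.75.

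**5. Can the better test be run with planned material?** Largely yes.

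- A resistance sample is taken at every visit (Section 2.5).
- Subjects with prior SVR whose HCV RNA reaches 1000 IU/mL have it tested (Section 1.7.1, footnote 5), and relapse samples at that level are sequenced (Section 2.5).
- Sequence data are transferred from the prior study (Section 3.2.4.1), though that does not guarantee a usable baseline sequence for every SVR subject.
- Rebounds from the LLoQ of 15 IU/mL to below 1000 IU/mL are not sequenced.

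**The case against.** **The intent is plain.** Section 3.5.3.1.1 cites Section 2.5 twice, and both mean to exclude reinfection. A reader might infer from the quoted sentence that even a recognised same-genotype reinfection must be counted as relapse. The documents do not support that, because the parenthesis and Section 2.5 would both exclude it. What stands is that the texts conflict for a recognised case, and that no test is named that would recognise one.

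**Consequences are limited.** This is correct. Section 3.5.5 rules out hypothesis testing. Sections 2.7.1.1 and 3.5.3.1.1 also report the percentage of subjects remaining below LLoQ, which does not depend on the relapse or reinfection label. After Amendment 03, subjects outside PN052 who entered below LLoQ left after their next scheduled visit (Section 2.4.1.1), and Section 2.7.1.1 drops data from the start of new HCV therapy. Even so, the label defines the event in the Kaplan-Meier estimate for the first primary objective, and PN052 subjects are exempt from that discontinuation.

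**The month counts.** A reader might take 54 and 30 months as upper limits. They are not. Section 2.5 assesses late relapse at the entry visit too, and Section 3.5.5.1.1 allows relapse dated at entry; on that reading the counts would be 60 and 36. Objective 1 requires HCV RNA below LLoQ at entry, so the answer depends on which passage governs. None of these counts measures a change in the estimate.

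**The resistance analyses.** Section 2.7.3.1 says "Only subjects who experienced virologic failure (other than reinfection) will be included in these analyses" and gives no definition there. A reader might see a second undefined exclusion. Criterion 3 already defines reinfection for essentially that population, so only a cross-reference is missing.

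**Parts of the remedy are choices.** Treating reinfection as a competing event, or censoring at a slightly different date, would also be defensible.

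**Conclusion.** The point holds and should be fixed. Genotype, the only test tied to the endpoint, cannot deliver the exclusion that Sections 2.5 and 3.5.3.1.1 both intend, and the two sections disagree about a same-genotype reinfection that is recognised. The last-visit censoring rule adds a related gap for recognised reinfections.

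The two effects run in opposite directions. Their size and net direction cannot be determined, because the plan gives no reinfection rate, genotype mix or number of subjects (Section 3.5.7 leaves the sample size open). No decision rule is affected; what is at stake is how far the relapse curve can be read as durability. The conclusion rests on the wording alone and assumes no unstated procedure brings the criterion 3 comparison into endpoint classification.

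**What to change.** - **Definition.** In Sections 2.5 and 3.5.3.1.1, define reinfection after SVR by both limbs of exclusion criterion 3: a different genotype, or phylogenetic comparison with the prior-study baseline sequence that indicates reinfection. Any other confirmed HCV RNA at or above LLoQ is relapse. Use the sequences already planned at 1000 IU/mL or more and those transferred from the prior study.
- **Cross-references.** Point Tables 2 and 5 to this definition. In Table 3 and Section 2.7.3.1, a reference to criterion 3 is enough.
- **Censoring.** In Section 3.5.5.1.1, censor recognised reinfections no later than first detection of the new virus, for example at the last result below LLoQ, and tabulate them separately.
- **Indeterminate cases.** Where a same-genotype case cannot be sequenced or compared, because no sample after SVR reaches 1000 IU/mL or no usable baseline sequence exists, keep it as relapse in the primary analysis and censor it in one sensitivity analysis.

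The cost is an amendment to the wording, a sequence comparison for the confirmed cases and one extra analysis. No new samples are needed. Some cases will stay indeterminate, and for those genotype remains the only evidence.
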